## **IX. Statistical Analysis:**

### **Statistical methods:**

Categorical data will be represented as frequency (n) and percentage (%) and will be analyzed using chi square test. Numerical data will be explored for normality by checking the data distribution, calculating the mean and median values and using Shapiro-Wilk tests. If the data is found to be normally distributed, it will be presented as mean and standard deviation values and independent t-test will be used for the analysis. If the assumption of normality is found to be violated; the data will be presented as median and range values and will be analyzed using Mann-Whitney U test. The significance level will be set at  $p<0.05$  for all tests. Statistical analysis will be performed with R statistical analysis software version 4.3.2 for Windows.

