### ***PICOTS Elements:***

Patient/Problem	Patients that are eligible for implant placement within inclusion criteria.
Intervention	Zirconia-based composite customized healing abutment.
Comparator	Conventional composite customized healing abutment.
Outcome	Clinical evaluation of peri-implant soft tissue changes via pink esthetic score and papilla index. Biochemical assessment of IL-1 $\beta$ level in the gingival crevicular fluid using Periopaper strip.
Time	Baseline, 1,2 and 3 months after implantation.
Setting	Faculty of Dentistry, Ain Shams University.

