## **VII. Materials and Methods:**

- **Study Setting:** Faculty of Dentistry, Ain Shams University.
- **Sample Size Calculation:** A power analysis was designed to have adequate power to apply a two-sided statistical test of the null hypothesis that there is no difference would be found between different tested groups regarding pink esthetic score. By adopting alpha ( $\alpha$ ) and beta ( $\beta$ ) levels of (0.05) (i.e. power=95%) and an effect size (d) of (1.87) calculated based on the results of a previous study; the total required sample size (n) was found to be (18) cases (i.e., 9 cases per group). Sample size was increased to account for possible dropout during different follow up intervals to be (22) cases (i.e., 11 cases per group). Sample size calculation was performed using R statistical analysis software version 4.3.2 for Windows.
- **Eligibility criteria:**  

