**Inclusion Criteria:**
  1. Patients should be systematically free from any disease as according to Cornell Medical Index-Health Questionnaire (**Pendleton et al., 2004**).
  2. Both genders.
  3. Age from 20-50 years.
  4. Missing tooth to be restored with standard implant, with no need for additional bone and soft tissue augmentation procedures (**Beretta et al., 2019**).
  5. Implants primary stability ISQ  $\geq$  70 unites using the Osstell Mentor (**Baltayan et al., 2016**).
  6. Sound Mesial and distal neighboring teeth.
  7. At least 6 natural teeth remaining in the same arch .
  8. Mouth opening  $\geq$  30mm.
  9. Thick phenotype.

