### **2- Details of the interventions, testing and follow up:**

- Group I (Customized Zirconia-Based Composite Healing Abutment):  
11 patients will receive delayed implant and a customized zirconia-based composite healing abutment placed simultaneously with implant surgery.
- Group II (Customized Conventional Composite Healing Abutment):  
11 patients will receive delayed implant and a customized conventional composite healing abutment placed simultaneously with implant surgery.

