### **Clinical Parameters Included:**

#### **1-Clinical evaluation of soft tissue:**

Pink Esthetic Score (PES) and The Papilla Index will be evaluated and changes between the two groups will be compared at baseline, 1,2 and 3 months (*Almadani et al., 2023*).

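### Baseline PES is collected but left out of the analysis; adjusting for it would be a cheap gain in precision if it is scored before abutment placement and is at least modestly prognostic (minor)

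*Protocol*

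**What the plan says.** Section IX (Statistical methods) sets one rule for all numerical data. After a normality check, "independent t-test will be used for the analysis"; if normality fails, a Mann-Whitney U test is used. No covariate is named.

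PES is a primary outcome, together with the Papilla Index. The PICOTS table gives the assessment times as "Baseline, 1,2 and 3 months after implantation", and the section on clinical evaluation of soft tissue says that "changes between the two groups will be compared at baseline, 1,2 and 3 months". The sample size paragraph concerns a "two-sided statistical test of the null hypothesis" that "no difference would be found between different tested groups regarding pink esthetic score", with d = 1.87, 9 per arm, raised to 11 per arm for dropout.

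On timing, the interventions section describes a "customized zirconia-based composite healing abutment placed simultaneously with implant surgery" (the comparator abutment is placed at the same point), and the inclusion criteria describe the site as "Missing tooth to be restored with standard implant". No section says whether baseline PES is scored before or after the abutment goes in.

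**The concern.** In a trial of 22 patients, a pre-treatment measure of the primary outcome is often the cheapest source of precision available. Here it is collected, but the named tests do not use it. What is at stake is the width of the confidence interval for the PES difference, and power if the true effect is smaller than the very large d = 1.87 assumed.

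Two pieces of wording decide whether the baseline can be used:

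- **Timing.** A baseline scored after placement may already carry an effect of the abutment. Adjusting for it could then remove part of the treatment effect.
- **Tested quantity.** The text speaks of changes compared at visits that include baseline, where no change from baseline can exist.

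**Working it through.** **Inputs from the protocol (sample size paragraph).** Two-sided alpha 0.05, target power 95%, d = 1.87, n = 9 per arm required and 11 per arm recruited.

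**Assumptions (not in the protocol).** The correlation rho between baseline and follow-up PES is taken as 0, 0.3, 0.5 and 0.7. A smaller effect, d = 1.0, is used for illustration.

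**Step 1. The plan's own figure.** For the two-sample t-test on raw scores, the noncentrality is d × sqrt(n/2) on 2n - 2 degrees of freedom.

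- n = 8: 1.87 × sqrt(4) = 3.74, 14 df, power 93.5%
- n = 9: 1.87 × sqrt(4.5) = 3.97, 16 df, power 96.1%
- n = 11: 1.87 × sqrt(5.5) = 4.39, 20 df, power 98.6%

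Nine per arm is the smallest size that reaches 95%, so the stated 18 reproduces. At d = 1.0 the raw-score power is 51% (n = 9) and 61% (n = 11).

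**Step 2. ANCOVA.** Given the observed baselines, the variance of the adjusted difference in SD units is (1 - rho²) × (2/n) × (1 + F/(2n - 2)), where F follows an F(1, 2n - 2) distribution and represents chance baseline imbalance. The test has 2n - 3 df. Power is averaged over F.

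**Step 3. Expected 95% CI half-width.** This does not depend on the effect size. It is the t quantile, times the expected ratio of estimated to true SD, times the standard error. At n = 9:

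- Raw: 2.120 × 0.9845 × sqrt(2/9) = 0.984 SD
- ANCOVA at rho = 0: 2.131 × 0.9835 × sqrt(2/9) × 1.034 = 1.022 SD, where 1.034 is the average of sqrt(1 + F/16)
- ANCOVA at other rho: multiply 1.022 by sqrt(1 - rho²), giving 0.975, 0.885 and 0.730 at rho 0.3, 0.5 and 0.7

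**Results**

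| | Raw | rho 0 | rho 0.3 | rho 0.5 | rho 0.7 |
|---|---|---|---|---|---|
| CI half-width (SD), n = 9 | 0.984 | 1.022 | 0.975 | 0.885 | 0.730 |
| change against raw | | +4% | -1% | -10% | -26% |
| CI half-width (SD), n = 11 | 0.878 | 0.904 | 0.863 | 0.783 | 0.646 |
| change against raw | | +3% | -2% | -11% | -26% |
| Power, d = 1.87, n = 9 | 96.1% | 94.6% | 96.2% | 98.4% | 99.8% |
| Power, d = 1.87, n = 11 | 98.6% | 98.1% | 98.8% | 99.6% | >99.9% |
| Power, d = 1.0, n = 9 | 51% | 49% | 52% | 60% | 77% |
| Power, d = 1.0, n = 11 | 61% | 58% | 62% | 71% | 86% |

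**Step 4. Break-even.** Equal CI width at n = 9 needs rho = sqrt(1 - (0.984/1.022)²) = 0.27; at n = 11, sqrt(1 - (0.878/0.904)²) = 0.24. Equal power needs rho of 0.26 to 0.29 at n = 9 and 0.23 to 0.26 at n = 11, the higher value in each pair being for d = 1.87. The overall range is about 0.23 to 0.29.

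**Step 5. Bounded score.** PES is a sum of seven items scored 0 to 2, so it runs from 0 to 14. With integer scores clipped to that range, n = 9, and an assumed SD of 1.5, baseline mean of 8 and control mean of 9.5, simulated power at d = 1.87 was about 95% raw, against 94.0, 95.4, 97.8 and 99.7% for ANCOVA at the four correlations. With the control mean at 11, near the ceiling, it was about 94% raw against 92.9, 94.3, 97.1 and 99.3%. The ANCOVA type I error stayed near 5% (about 0.047 to 0.052), also close to the ceiling, under assumed means and SDs.

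**The case against.** The strongest reply is that nothing here is an error. An unadjusted two-sample test is valid in a randomised parallel trial, the sample size reproduces, and a covariate is often left to the SAP. That stands, and it caps the point at a minor improvement. It does not remove the point, because the protocol names its tests.

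Secondly, the benefit rests on facts that the protocol does not give. That also stands. At d = 1.87 and rho = 0.3 the gain is practically nil, and the largest power gains need both a smaller effect and a high correlation, each of them assumed.

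Thirdly, the two conditions may pull against each other. A baseline usable for adjustment is scored at a site with no tooth and no abutment, where papilla, contour and gingival level may say little about the later score. The eligibility criteria (thick phenotype, no augmentation, sound neighbouring teeth) also narrow the baseline spread. A correlation near or below break-even is therefore plausible, though not shown. The answer is that the loss is bounded and small.

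Fourthly, a normal-theory ANCOVA on a bounded ordinal sum would replace a plan that has a non-normality route. This is fair, and the fix needs such a route too. The Papilla Index, also primary and also scored at baseline, was not part of these calculations; the point is confined to PES, the powered outcome.

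A reader might also infer from the word *changes* that change from baseline is the tested quantity and that the stated power may therefore fail. The protocol does not support this. The null hypothesis is on PES itself, the comparison includes the baseline visit, and Section IX names no change score. Raw scores compared at each visit is the most coherent reading.

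**Conclusion.** Minor: a cheap, conditional improvement. The planned test is valid and the stated power is correct for raw scores, taking d = 1.87 as given. A reader might infer an invalid analysis or an underpowered trial; neither follows.

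The gain requires both a baseline scored before placement and a correlation above about 0.23 to 0.29. If both hold, the CI at 9 per arm narrows by about 1, 10 or 26% at correlations of 0.3, 0.5 or 0.7. At the planned effect, power changes by about -1.5 to +4 points at 9 per arm and -0.5 to +1 at 11 per arm over the assumed range. It matters mainly if the true effect is well below 1.87: at an assumed d = 1.0 and 11 per arm, power goes from 61% unadjusted to 58, 62, 71 or 86%. The loose wording on timing and on the tested quantity would not be a finding alone; it matters because it decides whether the adjustment is legitimate.

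**What to change.** **Clinical evaluation section.** State that baseline PES is scored before abutment placement, if that is so, and replace the wording about changes with the score that is tested.

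**Section IX, if baseline is pre-placement.** Analyse PES at the visit the sponsor chooses by ANCOVA of the follow-up score on arm and baseline PES, and report the adjusted mean difference with its 95% CI. Keep the planned t-test or Mann-Whitney test as a sensitivity analysis. Use a rank-based ANCOVA if the residuals are clearly non-normal.

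**If baseline is post-placement.** Do not adjust. Keep the planned test on the raw score at the chosen visit; only the wording is clarified.

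**IL-1β.** It is sampled only at 2 months, has no baseline, and stays unadjusted.

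**Cost.** A few sentences, with no new visits or data; R, already named, fits the model. The statistical price is one degree of freedom. In the worst case shown (rho = 0, 9 per arm), the CI widens by about 4% and power falls by about 1.5 points at d = 1.87 or about 3 points at d = 1.0.

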## **X. Funding of the Study:**

This study will be personally funded by the researcher.

